2.0 Objectives*

In order to develop effective substance use intervention models for HIV care settings the specific aims of the current project are:

Aim1: Examine the feasibility of implementing the SBIRT-PN model in Infectious Disease-Medical Specialties Clinics in the state of Florida.

H1: We hypothesize that the SBIRT-PN model will demonstrate high feasibility as evidenced by at least 80 % of the total N having screenings.

Aim2a: Assess the acceptability of SBIRT-PN.

H2a: We hypothesize that SBIRT-PN will demonstrate high acceptability among patients enrolled in this condition.

Aim2b: Assess the acceptability of SBIRT-PN among HIV-positive individuals by age cohort (younger vs older).

H2b: We hypothesize that SBIRT-PN will demonstrate higher acceptability among older HIV-positive patients enrolled in this condition.

Aim3: Assess influence of SBIRT-PN model on treatment engagement and substance use compared to enhanced treatment as usual (TAU).

H3: We hypothesize that those in the SBIRT-PN condition will evidence greater treatment engagement and a reduction in substance use.

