3.0 Background*

Substance use science-to-service gap needs to close for the underserved aging with HIV. Many effective interventions do not translate into meaningful outcomes that improve patient care. Therefore, NIDA and the Office of AIDS Research have prioritized research that promotes the uptake of evidence-based interventions into real-world settings. In order to provide effective patient-centered care, effective interventions need to reach those in need. In particular, substance use interventions have lagged in moving from the bench (research labs) to the community (real-world settings). Extant literature suggests that peer navigators may improve treatment engagement among substance users and thereby has the potential to improve the effectiveness of SBIRT in this population in particular.

Florida provides the opportunity to implement substance use interventions among older HIV-positive adults. In Florida 42% of people living with HIV are aged 50 years and older compared to 31% in the rest of the United States. While cART has transformed HIV into a manageable chronic condition, leading to a large population aging with the disease, people aging with HIV continue to engage in high risk behaviors. At this stage in the HIV epidemic, we must use available evidence-based tools to meet the needs of those aging with HIV. Older adults living with HIV misuse alcohol and illicit drugs at rates higher than the general population. In addition, HIV+ adults aged 50 years and older are likely to be frailer than their chronological age indicates due to their

PROTOCOL TITLE: Feasibility of Brief Intervention for HIV+ Adults 50+ in Primary Care Settings

disease status, which makes them more vulnerable to the consequences of substance misuse (i.e., greater intoxication even with lower levels of consumption). Further, substance misuse is associated with decreased medication adherence, decreased engagement in HIV care, more medical co-morbidities, higher rates of depression, and poorer quality of life. Extant research suggests depression and pain are considered motivators of misuse and may make patients less responsive to interventions.

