17.0 Data Management* and Confidentiality

Analysis Plan

Aim 1: Feasibility will be calculated as described above. The model will be considered feasible if 80% of the target population has been reached.

Aim 2: Acceptability scores will be calculated for all participants as listed above to determine overall acceptability of the SBIRT model. Sub analyses will be conducted for disease type and HIV x age using calculations listed above. Acceptability will be examined by disease type HIV vs. non-HIV. Acceptability will also be examined for HIV only by younger (<49) versus older (>50).

Aim 3: This pilot is a randomized two groups (SBIRT-PN vs. TAU) with repeated measures (baseline and 3 and 6-month follow-ups) design. We will clean the data, examine variable distributions, compute descriptive statistics, examine outliers, and examine the effectiveness of randomization prior to analyses of specific aims to ensure the underlying assumptions of normality and equal variance have not been violated. Before testing each secondary outcome, we will examine whether intervention and control group participants differ on potential confounding variables at study entry. We will control for a variable if it differs by condition on the outcome variable being tested in that analysis at $p < .05$. Using chi-square (or t-test for continuous variables) we will examine the associations between the dependent variables and relevant demographic variables. All analyses will employ an intent-to-treat approach.

Our first step will be to see if the intervention influenced formal engagement in substance use treatment. Using chi-square analyses we will examine group difference on engagement in formal treatment (0=no treatment/1=treatment confirmed). To test the remainder of the hypothesis, analyses will rely on mixed model repeated measures ANOVA since the relatively small sample size is likely to prohibit more sophisticated statistical modeling. Hypotheses testing rely on inspection of F values and associated p values. A mixed model ANOVA is used to test for differences between two or more independent groups while subjecting participants to repeated measures. In the current analyses the fixed effect will be group condition (SBIRT-PN or TAU) and the random effect will be number of drug use days in the past 3 and 6 months.

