To examine ratings of acceptability, we will use the overall acceptability score and percentage of acceptability. Overall acceptability will be assessed by summing ratings from the 10-item questionnaire to provide a total intervention acceptability score for the intervention, such that acceptability scores for the intervention could range from 10 (low acceptability) to 50 (high acceptability). The intervention will be considered to have acceptability if 80% of the participants rank the intervention as acceptable (i.e., 4 or higher) on 80% or more of the scale items. We will then examine each question of the Acceptability Questionnaire separately to determine strengths and weaknesses of the intervention.

Aim 2a and 2b (Acceptability): Acceptability scores will be calculated for all participants as listed above to determine overall acceptability of the SBIRT model. Sub analyses will be conducted for disease type and HIV x age using calculations listed above. Acceptability will be examined by disease type HIV vs. non-HIV. Acceptability will also be examined for HIV only by younger (≤ 49) versus older (≥ 50).

Aim 3: We will clean the data, examine variable distributions, compute descriptive statistics, examine outliers, and examine the effectiveness of randomization prior to analyses of specific aims to ensure the underlying assumptions of normality and equal variance have not been violated. Before testing each secondary outcome, we will examine whether intervention and control group participants differ on potential confounding variables at study entry. We will control for a variable if it differs by condition on the outcome variable being tested in that analysis at $p < .05$. Using chi-square (or t-test for continuous variables) we will examine the associations between the dependent variables and relevant demographic variables. All analyses will employ an intent-to-treat approach.

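### H2b says older patients will find SBIRT-PN more acceptable than younger ones, but the plan specifies no older-versus-younger contrast, interval or criterion for 'higher'

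*SAP*

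**What the plan says.** Protocol 2.0 states H2b as a comparison: "We hypothesize that SBIRT-PN will demonstrate higher acceptability among older HIV-positive patients enrolled in this condition". Acceptability is listed under the primary outcome in Protocol 4.0.

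For the analysis, the SAP (Aim 2a and 2b) and Protocol 17.0 (Aim 2) say: "Sub analyses will be conducted for disease type and HIV x age using calculations listed above". The calculations referred to are:

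- a total score over ten items, ranging from 10 to 50;
- a pass/fail rule: "The intervention will be considered to have acceptability if 80% of the participants rank the intervention as acceptable", where a participant counts if the items are rated 4 or higher on at least 80% of the scale;
- a separate look at each item.

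The age groups are printed in two ways. The SAP has "Acceptability will also be examined for HIV only by younger (≤ 49) versus older (≥ 50"; Protocol 17.0 has "Acceptability will also be examined for HIV only by younger (<49) versus older (>50".

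**The concern.** H2b is a statement about a difference, and every listed calculation describes one group at a time. Neither document names an older-minus-younger estimate, a test, an interval, a significance level, or what would count as 'higher'. The sentence on chi-square and t-tests for demographic variables belongs to the Aim 3 covariate screening and is not tied to acceptability. Aim 3 does name its between-group analyses, so the gap is specific to Aim 2b.

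Followed as written, H2b would be supported or rejected on two point figures, or two pass/fail verdicts, with no measure of uncertainty. Which of these decides (total score, percentage or verdict) could be chosen after the data are seen.

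**Working it through.** The documents give no sample size, power or error rate for Aim 2b, so there is no figure of the plan to reproduce. The check asks how the only stated decision rule behaves if it is used to compare the age groups.

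**Inputs**
- SBIRT-PN arm: 90 patients (Protocol 10.0), equal allocation (Protocol 6.0, Randomization), so 90/2 = 45.
- Age split: an assumption, since there is no age quota. Protocol 3.0 says "In Florida 42% of people living with HIV are aged 50 years and older"; 0.42 × 45 = 18.9, so 19 older and 26 younger. A near-even 22/23 split is also shown.
- All 45 are assumed to answer the questionnaire; dropout is considered below.
- True acceptability rates are assumed and varied.

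**Method**
A group of n passes if at least 80% of its members count as accepting, so the cut-off is 0.8n rounded up: 16 of 19, 21 of 26, 18 of 22, 19 of 23. Let a and b be the exact binomial pass probabilities of the older and younger group.
- Different verdicts = a(1−b) + b(1−a)
- Older pass, younger fail = a(1−b)

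**Equal true rates**
Example at 80%, 19/26: a = 0.455, b = 0.577 (0.5775 before rounding). Different verdicts = 0.455 × 0.4225 + 0.5775 × 0.545 = 0.507.

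| True rate in both groups | Different verdicts, 19/26 | Different verdicts, 22/23 |
|---|---|---|
| 65% | 12% | 12% |
| 70% | 25% | 26% |
| 75% | 42% | 42% |
| 80% | 51% | 50% |
| 85% | 38% | 37% |
| 90% | 15% | 13% |
| 95% | 1.5% | 0.9% |

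**H2b true: older pass, younger fail**
Example at 90% versus 80%, 19/26: a = 0.885, b = 0.5775, so 0.885 × 0.4225 = 0.374; both pass in 0.885 × 0.5775 = 0.511.

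| Older vs younger | Position relative to 80% | 19/26 | 22/23 |
|---|---|---|---|
| 90 vs 80 | touches | 37% | 47% |
| 95 vs 85 | both above | 18% | 26% |
| 75 vs 60 | both below | 26% | 32% |
| 85 vs 75 | straddles, 10 points | 45% | 56% |
| 85 vs 70 | straddles, 15 points | 57% | 67% |
| 90 vs 75 | straddles, 15 points | 59% | 67% |
| 90 vs 70 | straddles, 20 points | 74% | 81% |

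**Dropout**
Protocol 25.0 expects 10% and at most 20% by the last visit. With 17/23 or 15/21, different verdicts at equal rates occur in 44–50% of trials at 75–80%, 31–38% at 85% and 10–14% at 90%.

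**What a direct contrast would give**
- Mean total score, 95% CI half-width in SD units: t(43) × √(1/19 + 1/26) = 2.017 × 0.302 = 0.61; for 22/23, 2.017 × 0.298 = 0.60.
- Difference in proportions, both at 80%: 1.96 × √(0.16 × (1/19 + 1/26)) = 0.237; for 22/23, 0.234.
- Power for 90% versus 75% (normal approximation, two-sided 0.05, assumed): 23% at 19/26 and 26% at 22/23. Power of 80% would need 100 per age group.

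**The case against.** Several objections have force.

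- *The plan never says that discordant verdicts mean an age effect.* True. The 80% rule judges the intervention, and the total score and percentage can be compared descriptively. A reader might infer that the trial cannot address Aim 2b at all. That goes too far: the aim is to assess acceptability by age cohort, which descriptive figures do. What stands is that H2b claims a direction and no comparison with uncertainty is specified for it.
- *The error rates depend on the assumed truth.* Also true. A reader might infer that equal groups generally get different verdicts, or that a real difference is usually missed. The first holds only near 80%. The second fails for gaps of 15–20 points that straddle 80%, where an older-only pass occurs in 57–81% of trials.
- *The rounding of the cut-off looks like an unequal hurdle* (16/19 = 84.2% against 21/26 = 80.8%). This comes from the assumed split and disappears at 20/25, where both cut-offs are exactly 80%. It is not a defect of the plan.
- *The age limits may be a printing matter.* The protocol's < and > could be ≤ and ≥ that lost a stroke in PDF reading. The SAP's groups are exhaustive, so it cannot be concluded that patients aged 49 or 50 are left out.
- *A direct comparison is weak at this sample size.* It is. That argues for an estimate with an interval and an exploratory label, not for leaving the contrast undefined.

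**Conclusion.** The concern stands in limited form. H2b is a between-group hypothesis on a primary outcome, and the plan supplies only within-group calculations for it. Used as a substitute for a comparison, the 80% rule separates truly equal groups in about 37–51% of trials when the common rate is 75–85%. It shows an older-only pass in fewer than half of trials when the two rates lie on the same side of 80% or touch it.

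These sizes rest on 45 respondents in the SBIRT-PN arm, a 19/26 or 22/23 age split, and the true rates shown. The 42% behind the first split is a statewide figure, not a recruitment target. Away from 80%, false discordance is 15% or less for these two splits (at 90% and above, or 65% and below). The absence of a stated contrast depends on none of these assumptions.

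**What to change.** State in the SAP, under Aim 2b:

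- H2b is assessed in the SBIRT-PN arm by the difference (≥50 minus ≤49) in mean total acceptability score, with its 95% CI.
- The difference in the proportion meeting the acceptability criterion is reported with its 95% CI.
- H2b is exploratory, because the intervals will be wide: about ±0.6 SD for the score, and about ±23–24 percentage points for the proportion when both rates are 80%.
- The 80% rule is not a test of H2b.

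Naming the arm also settles a side issue: H2b concerns the SBIRT-PN condition, while the SAP speaks of scoring all participants. Reconcile the age limits printed in Protocol 17.0 (<49 / >50) with those in the SAP (≤49 / ≥50).

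The cost is wording in two documents; the questionnaire and the age groups are already planned, so no new measure is needed. The downside is a less favourable statement on H2b, since the wide intervals will often leave the direction open.

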Substance Use Treatment Engagement: Participants will self-report if they obtained formal substance use treatment (i.e., any services sought to address substance use from individual therapy to 12 step fellowships). We will request treatment facility information and permission to verify treatment. Once treatment has been verified, treatment engagement will be coded as 0= no formal treatment 1= formal treatment engagement

Substance use NIDA STTR Drug and Alcohol Use Measure: A standard measure from the NIDA STTR Vulnerable Populations Data Harmonization tool kit will be used. It will assess quantity and frequency of types of substances used in the prior 30 days.

Biologically Confirmed Drug Use: A CLIA 12-Panel Instant Drug Test Cup (CLIAwaived™, San Diego, CA), which tests for the presence of 12 common substances in the urine will be used.

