6.0 Procedures Involved*

Recruitment/Sampling: Patients will be recruited using convenience sampling technique from HIV primary care clinics with whom the PI works regularly: the Columbia County Department of Health (Lake City, FL) and the CAN Community Health Clinic (Jacksonville, FL)

Preliminary Screen: Patients will be prescreened for eligibility using a computerized screening tool, NIDA Modified Alcohol, Smoking, Substance Involvement Screening Test [NM-ASSIST], to assess substance misuse risk level. All clinic patients will have the opportunity to complete the substance use screening assessment after checking in for their appointment. All who score moderate and above on the alcohol or illicit substance portion of the NM-ASSIST and meet eligibility criteria will be referred to the study. We will train all recruiters (clinic staff) to provide an extensive explanation of why we are offering these services, as the patients may not perceive themselves as having a substance misuse issue.

Baseline Assessment Procedures: Following a successful initial screen, study staff will explain the procedures of the study and obtain informed consent. All study activities will be conducted in a private room in the clinic. The research assistant (RA) performing the assessment will verify the patient's complete understanding of the informed consent form and all study procedures. Following informed consent, patients will complete the baseline assessment. The baseline assessment will consist of urine drug screen and a series of research questionnaires delivered on a mobile device. The research questionnaires include information on: substance use, substance use treatment, HIV treatment engagement, depression, and pain. The assessment is relatively brief in order to maximize willingness to participate and decrease patient burden. The assessment will take approximately 30 minutes to complete. The questionnaires will be given in a computerized. The iPad/tablet will use REDCap survey software, which provides direct, encrypted transfer of information via internet to a secure study server.

Three and Six Month Follow-Up Assessment: *Participants will be contacted three and six months post-intervention to schedule an in-person follow-up assessment. We will evaluate substance use treatment engagement post intervention and substance use (self-report and urine toxicology analysis). Participants will be compensated \$30 for each*

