Randomization: We will use Block random assignment (blocks of 4 by each recruitment site) to ensure equal numbers are assigned to each condition by site. Randomization should create groups with equal characteristics with respect to disease related and medical variables. However, we will assess for baseline differences prior to conducting any analyses and control as necessary.

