Our first step will be to see if the intervention influenced formal engagement in substance use treatment. Using chi-square analyses we will examine group difference on engagement in formal treatment (0=no treatment/1=treatment confirmed). To test the remainder of the hypothesis, analyses will rely on mixed model repeated measures ANOVA since the relatively small sample size is likely to prohibit more sophisticated statistical modeling. Hypotheses testing rely on inspection of F values and associated p values. A mixed model ANOVA is used to test for differences between two or more independent groups while subjecting participants to repeated measures. In the current analyses the fixed effect will be group condition (SBIRT-PN or TAU) and the random effect will be number of drug use days in the past 3 and 6 months.

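### Aim 3 selects covariates by a p < .05 difference between arms and pre-specifies neither the baseline outcome nor site, which costs precision

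*SAP*

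**What the plan says.** The SAP (Aim 3) and Protocol 17.0 (Analysis Plan, Aim 3) compare the arms on possible confounders at entry before each secondary outcome is tested. Both then state: "We will control for a variable if it differs by condition on the outcome variable being tested in that analysis at" p < .05. Protocol 6.0 (Randomization) has a looser version: "we will assess for baseline differences prior to conducting any analyses and control as necessary".

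The allocation scheme in the same section is "Block random assignment (blocks of 4 by each recruitment site"). The model sentence, in both documents, is that "the fixed effect will be group condition (SBIRT-PN or TAU) and the random effect will be number of drug use days", specifically "number of drug use days in the past 3 and 6 months". Treatment engagement is compared between arms by a plain chi-square test.

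On baseline data, Protocol 6.0 says "The baseline assessment will consist of urine drug screen and a series of research questionnaires delivered on a mobile device", and the questionnaires cover substance use. Protocol 4.0 says of the self-report measure: "It will assess quantity and frequency of types of substances used in the prior 30 days". The urine cup "tests for the presence of 12 common substances in the urine".

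No section of either document names the baseline outcome or site as a covariate.

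**The concern.** In a properly randomised trial, any baseline difference between arms is due to chance. A significance test of that difference therefore says nothing about whether the variable predicts the outcome, and prediction is what makes adjustment worthwhile. A p < .05 screen discards the likely best predictor, the baseline value of the same measure, in about 19 trials out of 20. It also leaves the model undetermined until the data are seen.

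Three ambiguities add to this.

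- **The rule.** It speaks of a variable differing by condition on the outcome being tested. That can be read as a baseline imbalance test, as a test involving the outcome, or as both.
- **The role of baseline.** Protocol 1.0 and 17.0 list it as one of the repeated measurements, but the model sentence mentions only 3 and 6 months.
- **The window.** The model sentence counts days over 3 and 6 months, while the instrument covers 30 days. A baseline value of the same measure exists only if the 30-day window is the outcome.

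At stake is the precision of the drug-use-days and urine comparisons in Aim 3, which the plan itself describes as a small sample.

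**Working it through.** The plan gives no Aim 3 power figure to reproduce.

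**Inputs from the documents.** N = 90 in two equal arms, so 45 per arm. Dropout is 10% expected and 20% at most (Protocol 25.0, Retention): 45 × 0.9 = 40.5, taken as 40, and 45 × 0.8 = 36.

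**Assumptions, not in the documents.** True effect 0.5 SD; two-sided 0.05; normal outcomes with equal variances; baseline-to-follow-up correlation r = 0.3, 0.5 or 0.7; with two follow-ups, all pairwise correlations equal to r.

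**Variance of the treatment effect, relative to one unadjusted follow-up**

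| Analysis | One follow-up | Mean of two follow-ups |
|---|---|---|
| Baseline not used | 1 | (1 + r)/2 |
| Baseline as a time level (change contrast) | 2(1 − r) | 1.5(1 − r) |
| Baseline as covariate | 1 − r² | (1 + r)/2 − r² |

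For one follow-up the covariate row is 0.91 / 0.75 / 0.51 and the change row 1.40 / 1.00 / 0.60. The covariate analysis has the smallest variance at every r.

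**Hand check, 40 per arm.** Power ≈ Φ(0.5·√(40/2)/√v − 1.96) = Φ(2.236/√v − 1.96). With v = 1 this is Φ(0.276) = 61%. With v = 0.75 it is Φ(0.622) = 73%.

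**Simulated power, 40,000 runs per cell.** The rule is an unadjusted comparison unless the baseline t-test gives p < .05, in which case baseline is added.

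| Setting | r | Rule, baseline otherwise unused | Change contrast | Baseline covariate |
|---|---|---|---|---|
| One follow-up, 40 per arm | 0.3 | 60.3% | 46.5% | 63.3% |
| | 0.5 | 60.3% | 59.4% | 71.3% |
| | 0.7 | 61.3% | 81.1% | 86.6% |
| One follow-up, 36 per arm | 0.3 | 55.3% | 42.4% | 58.5% |
| | 0.5 | 55.6% | 55.0% | 66.7% |
| | 0.7 | 56.5% | 76.9% | 82.5% |
| Two averaged, 40 per arm | 0.3 | 78.8% | 58.3% | 83.6% |
| | 0.5 | 73.6% | 72.2% | 87.3% |
| | 0.7 | 69.1% | 90.9% | 95.7% |

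Repeat runs with other seeds agree to within about one point. For one follow-up at 40 per arm, the covariate gains 3.0 / 11.0 / 25.3 points over the rule and 16.8 / 11.9 / 5.5 points over the change contrast.

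**How often the rule selects baseline (one follow-up, 40 per arm).** Read as a difference by condition: 5.1 / 4.9 / 5.1% of trials. Read as requiring an association with the outcome as well: 3.6 / 4.9 / 5.1%, with power 60.1 / 60.3 / 61.3%. Only a reading that drops the by-condition requirement selects baseline often (75.5 / 99.6 / 100%).

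**Type I error under the rule:** 4.8 / 4.2 / 3.8%. It is not inflated.

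**Can the rule select site?** With blocks of 4, the arms within a site can differ by at most 2. Over all splits of 90 between two sites (at least 5 each), the most extreme table is 4 v 2 at one site and 42 v 42 at the other: χ² = 90 × (4×42 − 2×42)² / (6×84×46×44) = 635,040 / 1,020,096 = 0.62, p = 0.43. So it cannot, as randomised.

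**Value of site for drug-use days (two follow-ups averaged, baseline already in the model).** No measurable cost if the sites are alike. If they differ by 0.5 SD, power rises from 82.5 to 83.9% at r = 0.3 and by less at higher r.

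**Urine result, coded positive/negative** (assumed 60% positive at baseline, 60% v 35% at one follow-up, 40 per arm, phi 0.33 / 0.53 / 0.71). Rule 64.2 / 64.4 / 65.2%; logistic model with baseline and site 65.9 / 73.7 / 79.3%.

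**Engagement** (assumed 25-point effect, 20 per arm per site). Chi-square v Mantel-Haenszel: 79.3 v 79.4% with control rates of 10% at both sites, 67.3 v 69.3% with 10% and 30%, and 66.0 v 73.6% with 5% and 45%.

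**The case against.** The strongest counter-argument is that Aim 3 is a secondary aim of a pilot with no power claim. Type I error holds and the primary conclusions are unaffected, so what remains is an efficiency loss of unknown size. The two readings of baseline even move in opposite directions with r, so no single figure can be given. All of that is true, and it limits how serious the point is. It does not justify keeping the rule: H3 is still tested through F and p values, and a small trial can least afford to discard precision.

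A second argument is that Protocol 1.0 and 17.0 make baseline a repeated level, so it is already used, and a change contrast is a valid analysis. It is valid, but less precise than the covariate analysis at every r examined. At r = 0.3 it is worse than ignoring baseline (46.5% v 60.3%).

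Third, the sentence after the rule looks at associations between outcomes and demographic variables. An association-only rule would lose almost nothing (62.7 / 71.3 / 86.6% power). That sentence concerns demographics, however, and the rule itself requires a difference by condition. The imputation plan in Protocol 17.0 does not add a baseline covariate either.

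Several narrower points stand. Site contributes little. The largest engagement gain needs site rates for which the documents give no basis. The simulations use normal data and completers, whereas days in a 30-day window are bounded. The documents do not say how the 12-panel result will be coded.

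**Conclusion.** The concern holds. Whether baseline is left out or treated as a time level, Aim 3 as written is less precise than an analysis with the baseline value as a covariate, and the p < .05 rule recovers almost none of the loss. Under the assumptions above, with one follow-up and 40 per arm, the shortfall is about 3 to 25 points of power on the first reading and about 17 down to 5 on the second as r rises from 0.3 to 0.7. The size rests on an assumed effect and correlation; the direction does not depend on r within that range. Site belongs in the model mainly because allocation was blocked on it. For engagement the baseline argument does not apply, because patients already in addiction treatment are excluded (Protocol 10.0). This is a worthwhile improvement to a secondary analysis, not a threat to the trial's main conclusions.

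**What to change.** 1. Delete the p < .05 rule in the SAP (Aim 3) and Protocol 17.0, and the conditional adjustment clause in Protocol 6.0 (Randomization). Baseline comparisons may stay as description.
2. In both documents, replace the sentence naming group as the fixed effect and drug-use days as the random effect with:

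> For drug-use days, the 3- and 6-month values are the repeated outcomes; group, visit, group-by-visit, the baseline value of the same measure and recruitment site are fixed effects, with within-participant correlation modelled. The Aim 3 test is the group effect averaged over the two visits.

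3. State drug-use days over the instrument's 30-day window, so that baseline and follow-up are the same measure.
4. State how the urine result is coded. If positive/negative, use the corresponding logistic model with the baseline result and site.
5. Replace the plain chi-square for engagement with a site-stratified Mantel-Haenszel test.
6. Label any other covariate adjustment as a sensitivity analysis.

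The cost is rewording in Protocol 6.0, Protocol 17.0 and the SAP's Aim 3 text. No new data are needed if the 30-day window is the outcome, since the baseline visit already includes the urine screen and the substance-use questionnaire. Baseline and site use two model degrees of freedom. The gain is small if baseline correlates weakly with follow-up (unless baseline would otherwise be a time level), and site adds little if the clinics are similar.

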10.0 Subject Population*

Participants will be 90 patients recruited through DOH Columbia County and CAN Community Health.

Study inclusion criteria includes that patients must be:

1. HIV-positive (seropositive confirmed by medical records).
2. Arrive for a clinic visit with an HIV physician.
3. Have a substance misuse screening score indicating moderate or high risk.

Persons will be ineligible if they:

1. are unable to interview and consent in English
2. unwilling or unable to participate in follow up
3. currently in addiction treatment
4. have a medical marijuana prescription

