Attrition is a significant concern in an implementation trial. First, we will develop a strong collaborative relationship between participants and members of the research team. This is a critical component of our retention strategy, beginning at the moment of first contact between the recruiter and potential participant. Second, we will ensure that participants understand that they are making a contribution and that their efforts have the potential to improve other people's experiences. Participants will receive study newsletters and flyers containing useful and pertinent information on wellness management and other related resources and local events. Finally, we will obtain secondary contact information and will use multiple communication channels (email, phone, text messaging, social media) to maintain contact with study participants. We have budgeted research staff time for tracking and follow-up of participants. One RA will dedicate 20% time to patient tracking during recruitment and follow up phase. Based on our prior work using these strategies with this patient population, we anticipate a 10% dropout rate with a maximum dropout rate of 20% by time 3.

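### No effect estimate or confidence interval is planned for Aim 3, and the 80% acceptability verdict has no interval, so neither result can be read with known precision

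*SAP*

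**What the plan says.** Aim 3 (Protocol section 2.0) concerns the effect of SBIRT-PN against enhanced treatment as usual, and its hypothesis is directional: "We hypothesize that those in the SBIRT-PN condition will evidence greater treatment engagement and a reduction in substance use". The SAP gives two tests for it.

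- Engagement: "Using chi-square analyses we will examine group difference on engagement in formal treatment", coded as a binary outcome.
- Substance use: a mixed-model repeated-measures ANOVA, of which the SAP says "Hypotheses testing rely on inspection of F values and associated p values". Protocol section 17.0 has the same sentence.

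No between-arm estimate or interval is named for either outcome. Descriptive statistics are mentioned only as a step before the aims are analysed.

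Acceptability is a primary outcome in Protocol section 4.0. Its rule is: "The intervention will be considered to have acceptability if 80% of the participants rank the intervention as acceptable", where acceptable means a score of 4 or more on at least 80% of the items. No interval or reference value goes with the verdict.

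The sample size is given without derivation: "Participants will be 90 patients recruited through DOH Columbia County and CAN Community Health". The documents state no target effect, power or Aim 3 alpha. Section 17.0 calls the study a pilot, and the SAP itself describes the sample as relatively small.

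**The concern.** An F or chi-square statistic and its p-value give neither the size nor the direction of a difference, although H3 is about direction. In a small trial with no stated target effect, a p-value above .05 does not separate absence of influence from too few patients. It also hands the next trial no estimate to plan from, which is much of the purpose of a pilot.

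The acceptability verdict has a similar weakness. A pass or a fail at an observed 80% says nothing about the range of true rates that fit the data, and this verdict is one of the study's two primary results.

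**Working it through.** **Inputs from the documents**
- Total 90 (Protocol 10.0 and 12.0). Blocks of 4 by site are used "to ensure equal numbers are assigned to each condition by site" (6.0), so 90/2 = 45 per arm.
- Dropout: "we anticipate a 10% dropout rate with a maximum dropout rate of 20% by time 3" (25.0). At the maximum, 45 × (1 − 0.20) = 36 per arm.
- The only significance level in the SAP is p < .05 for choosing covariates ("We will control for a variable if it differs by condition on the outcome variable being tested in that analysis").

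**Assumptions:** two-sided alpha 0.05 for Aim 3; a range of standardised effects d; 10% engagement under treatment as usual; between-visit correlation 0.5 with compound symmetry where repeated measures are used. The figure of 90 cannot be reproduced, because no design inputs are given.

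**1. Precision of a mean difference, simple two-arm comparison.** Half-width in SD units = 1.96 × √(2/n).
- n = 36: 1.96 × 0.2357 = 0.46
- n = 45: 1.96 × 0.2108 = 0.41

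**2. Power of the same comparison**, Φ(d/√(2/n) − 1.96). It equals 50% where d equals the half-width above.

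| True d | 36 per arm | 45 per arm |
|---|---|---|
| 0.3 | 25% | 30% |
| 0.4 | 40% | 47% |
| 0.5 | 56% | 66% |
| 0.6 | 72% | 81% |
| 0.8 | 92% | 97% |

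**3. Dependence on the repeated-measures term.** Per-patient variances are in units of SD², with r = 0.5 and d = 0.5 at both follow-ups.
- Baseline-adjusted mean of two follow-ups: (1+r)/2 − r² = 0.50. Power is 85% (36) to 92% (45).
- Follow-up mean minus baseline: (1+r)/2 + 1 − 2r = 0.75. Power is 69% to 78%.
- Group main effect over all three visits: variance (1+2r)/3 = 0.667, with the effect diluted to 2d/3. Power is 41% to 49%.

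The SAP names only group as a fixed effect, and lists the number of drug-use days, which is the outcome, as the random effect. The term to be tested is therefore not fixed.

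**4. Engagement, 20% vs 10% (assumed).** Half-width = 1.96 × √[(0.2×0.8 + 0.1×0.9)/n], which is 16 points at n = 36 and 15 points at n = 45.

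**5. Acceptability.** Exact (Clopper–Pearson) 95% interval at the smallest count that passes, and the binomial chance of passing:

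| Raters | Just passes | Exact 95% CI | Passes if true 75% | 78% | 80% |
|---|---|---|---|---|---|
| 36 | 29 | 64%–92% | 29% | 45% | 57% |
| 45 | 36 | 65%–90% | 28% | 46% | 59% |
| 72 | 58 | 70%–89% | 17% | 36% | 52% |
| 90 | 72 | 70%–88% | 17% | 38% | 56% |

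The first two rows apply if the SBIRT-PN arm alone rates, as H2a in Protocol 2.0 implies. The last two apply if all participants rate, as the SAP text for Aims 2a and 2b says (72 = 90 × 0.80). None of these counts apply to the Aim 1 feasibility rule, whose target population is the clinic's patients seen during the study.

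**The case against.** The strongest reply is that this is a pilot whose primary outcomes are feasibility and acceptability. Lack of a power statement for a secondary aim is not in itself an error, and an observed-percentage threshold set in advance is a legitimate pilot criterion. The acceptability plan also goes beyond the threshold, with a 10–50 total score and item-by-item results. Missing data are to be imputed under intent to treat (Protocol 17.0), so 36 per arm is a completer count. All of this stands. Imputation does not restore full information, however, so the last point affects the range and not the direction.

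Two stronger readings are tempting, and the documents support neither.

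- *A real effect would usually be reported as no effect.* Neither document says that a non-significant result will be described that way, and no expected effect is stated. In the simple comparison an effect is missed more often than not only below about d = 0.41–0.46; at d = 0.5 it is detected in 56%–66% of trials. The planned analysis is a repeated-measures one, which could do better or worse, so no single failure rate can be quoted.
- *Borderline acceptability would be passed off as established.* With 36 to 45 raters, a true 75% fails the rule in 71%–72% of trials, and a true 80% still fails in 41%–43%. The fault is imprecision near the threshold, not routine false acceptance.

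**Conclusion.** The concern holds in this limited form: the plan supplies no estimate or interval by which to interpret Aim 3, and none for the 80% acceptability verdict. With 36–45 per arm, two-sided alpha 0.05 and a simple comparison, a result centred on zero would leave differences of up to about 0.41–0.46 SD in either direction unexcluded. An observed 80% is compatible with true acceptability from about 64% to 92% in the widest case and 70% to 88% in the narrowest. With 36–45 raters and a true rate of 78%–80%, passing is close to a coin toss (45%–59%).

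The acceptability point survives under either set of raters. The Aim 3 figures are illustrations, because they rest on an assumed alpha and on a simpler test than the one planned. This is a worthwhile improvement to the analysis plan and does not invalidate the design.

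**What to change.** Replace the sentence on F and p values in the SAP and in Protocol 17.0 with wording such as:

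*The Aim 3 result is the between-arm difference in days of use at follow-up with its 95% CI, and the risk difference in confirmed treatment engagement with its 95% CI. P-values are supportive. A p-value above .05 will not be read as absence of effect.*

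Define the model that yields the first estimate: days of use as the outcome; group, visit and group-by-visit as fixed effects; participant as the random effect. State the follow-up contrast to be reported.

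For acceptability, first reconcile whether the raters are the SBIRT-PN arm (H2a) or all participants (SAP, Aims 2a and 2b). Then report the 80% verdict with its exact 95% CI and word the conclusion by that interval.

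The cost is SAP and protocol wording plus a properly specified model. No further patients, visits or data are needed. The downside is that conclusions become less categorical.
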